11.3.2 VAS Knee Pain (0-100mm VAS)

The time point of main interest is 26 weeks, but in order to study the time course profile, the data will be analyzed at each time point. The average weekly pain score and the Area Under the weekly pain Curve (AUC) will be analyzed via an ANOVA and a mixed effects repeated measures ANOVA with a term for treatment and Baseline pain score as a covariate. The analysis will be conducted by constructing 95% confidence intervals using the predefined contrasts for comparing the Cingal® arm to the TH arm, the Cingal arm to the Placebo arm, and the TH arm to the Placebo arm.

11.3.3 NRS Knee Pain (0-10 NRS)

The time point of main interest is 26 weeks, but in order to study the time course profile, the data will be analyzed at each time point. The average weekly pain score and the Area Under the weekly pain Curve (AUC) will be analyzed via an ANOVA and a mixed effects repeated measures ANOVA with a term for treatment and Baseline pain score as a covariate. The analysis will be conducted by constructing 95% confidence intervals using the predefined contrasts for comparing the Cingal® arm to the TH arm, the Cingal arm to the Placebo arm, and the TH arm to the Placebo arm.

11.3.4 WOMAC Physical Function change from Baseline

The time point of main interest is 26 weeks, but in order to study the time course profile, the data will be analyzed at each time point. Data will be analyzed via an ANOVA with a term for treatment and Baseline score as a covariate. The analysis will be conducted by constructing 95% confidence intervals using the predefined contrasts for comparing the Cingal® arm to the TH arm, the Cingal arm to the Placebo arm, and the TH arm to the Placebo arm.

11.3.5 WOMAC Stiffness score change from Baseline

The time point of main interest is 26 weeks, but in order to study the time course profile, the data will be analyzed at each time point. Data will be analyzed via an ANOVA with a term for treatment and

Baseline score as a covariate. The analysis will be conducted by constructing 95% confidence intervals using the predefined contrasts for comparing the Cingal® arm to the TH arm, the Cingal arm to the Placebo arm, and the TH arm to the Placebo arm.

11.3.6 Total WOMAC score change from Baseline

The time point of main interest is 26 weeks, but in order to study the time course profile, the data will be analyzed at each time point. Data will be analyzed via an ANOVA with a term for treatment and Baseline score as a covariate. The analysis will be conducted by constructing 95% confidence intervals using the predefined contrasts for comparing the Cingal® arm to the TH arm, the Cingal arm to the Placebo arm, and the TH arm to the Placebo arm.

11.3.7 Patient Global Assessment change from Baseline

The time point of main interest is 26 weeks, but in order to study the time course profile, the data will be analyzed at each time point. Data will be analyzed via an ANOVA with a term for treatment and Baseline score as a covariate. The analysis will be conducted by constructing 95% confidence intervals using the predefined contrasts for comparing the Cingal® arm to the TH arm, the Cingal arm to the Placebo arm, and the TH arm to the Placebo arm.

11.3.8 Evaluator Global Assessment change from Baseline

The time point of main interest is 26 weeks, but in order to study the time course profile, the data will be analyzed at each time point. Data will be analyzed via an ANOVA with a term for treatment and Baseline score as a covariate. The primary analysis will be conducted by constructing 95% confidence intervals using the predefined contrasts for comparing the Cingal® arm to the TH arm, the Cingal arm to the Placebo arm, and the TH arm to the Placebo arm.

11.3.9 Rescue Medication Usage

The time point of main interest is 26 weeks, but in order to study the time course profile, the data will be analyzed at each time point. Data will be analyzed via an ANOVA with a term for treatment and Baseline score as a covariate. The primary analysis will be conducted by constructing 95% confidence intervals using the predefined contrasts for comparing the Cingal® arm to the TH arm, the Cingal arm to the Placebo arm, and the TH arm to the Placebo arm.

11.5 Statistical Methods

Tabulation of summary statistics, graphical presentations, and statistical analyses will be performed using SAS® software 9.1.3 or higher version. Where not otherwise specified, the last pre-treatment observation will be used as Baseline for calculating post-treatment changes from Baseline. The primary presentations and analyses will be based on data pooled across study centers. Relevant summaries for individual centers, or combinations of centers, may be presented for primary data. All confidence intervals will use a significance level of 5%.

11.6 Demographic and Baseline Characteristics

All demographic and Baseline characteristics will be tabulated by treatment arm and a test of homogeneity between the treatment arms will be conducted. For continuous variables (e.g. age, height, weight) a one-way ANOVA will be used. For categorical variables (e.g. gender, race), a Fisher's exact test or chi-squared test will be used. Medical History findings, Physical Exam and Concomitant Medications will be tabulated by treatment arm.

The Baseline Chemistry, Hematology, Urinalysis, Vital Signs, and BMI data will be summarized via descriptive statistics and tested for homogeneity using a one-way ANOVA.

11.7 Adverse Events

All AEs will be coded according to MedDRA. Safety assessments will include Treatment-Emergent Adverse Events (TEAEs) which are defined as AEs with an Investigator assessment of definitely,

probably, or possibly related to CTM/study procedure. TEAEs will be summarized with frequencies and percentages by system organ class and preferred term, severity, and relationship to study CTM/study procedure for each treatment arm. In summaries of TEAEs by severity and relationship to CTM/study procedure for subjects reporting multiple episodes, all reported events will be included, not only the worst reported case. Serious Adverse Events will also be presented by relationship to the CTM/study procedure.

The number of subjects with at least one AE will be tabulated for each treatment arm. Differences between the treatment arms will be tested using Fisher's exact test. Then the number of AEs for each treatment arm will also be tabulated.

The number of subjects and the number of AEs will be tabulated by severity, relationship, and local injection site specific events versus non local events.

11.8 Subject Populations

All safety analyses will be conducted on all subjects who undergo treatment in any arm.

The primary analysis on the primary endpoint will be performed on the ITT populations using the Multiple Imputation Methodology. The Multiple Imputation Methodology will use a mixed effects repeated measures model to predict the missing values. All Primary and Secondary endpoints will be analyzed using the ITT population.

It has been determined that any missing data in this study will follow the Missing at Random (MAR) assumption and is justified by the following section from the guide on missing data [31].

11.9 Additional Analyses

All of the analyses are performed on the data without covariates or other factors assumed in the model. If it is determined that certain factors may influence the outcomes of the endpoints, then additional analyses will be performed. For the continuous variables, the factors will be added to the ANOVA model and evaluated in a stepwise fashion for significance. For the discrete variables, the data will be analyzed via a GEE model with the factors added to the model.

12 DATA MANAGEMENT CONSIDERATIONS

12.1 Electronic Data Capture (EDC) System

The EDC system to be used in this study will be 21CFR part 11 compliant and have appropriate Quality Management Systems in place.

All sites will receive appropriate training on using the EDC System including completing the eCRF and responding to queries. Each designated site participant will receive a unique electronic signature: consisting of a username and password, after training has been completed in order to access the EDC System.

12.2 Data Collection

One eCRF will be completed for each study Subject based on the source documents. Once a Subject's eCRF has been completed by the site, the data management group will begin the data cleaning process. The details of completing the eCRF by the site can be found in the eCRF Completion Guidelines.

12.3 Data Management

Once the eCRF is ready for review, the data management group will complete automated and manual validation checks according to the Data Management Plan (DMP) to ensure the quality, consistency, and completeness of all data entered. Instances of incomplete, uninterpretable or inconsistent data will be resolved with the site through issuing a query or other means of communication as necessary. The site is responsible to respond and / or correct the data for all queries issued in a timely manner. All queries and changes to the data will be tracked.

12.4 Data Retention

At the end of the study, an electronic transfer of all data will be provided to the Sponsor. The Contract Research Organization (CRO) and Sponsor will be responsible for retaining all data and documents pertaining to this study for a period of at least 2 years after the Cingal FDA marketing application is approved; or, if an application is not approved for Cingal, until 2 years after shipment and delivery of the drug for investigational use is discontinued and FDA has been so notified; or as required by local applicable regulatory requirements.

The Sponsor will be responsible for retaining the final data set and documents pertaining to this study for a period of at least 2 years after the Cingal FDA marketing application is approved; or, if an application is not approved for Cingal, until 2 years after shipment and delivery of the drug for investigational use is discontinued and FDA has been so notified; or as required by local applicable regulatory requirements.

13 CLINICAL SUPPLIES

13.1 Packaging and Labeling

CTM will be provided enclosed in a carton containing required labeling and caution statements and a unique identifying kit number. An independent third party will maintain the master randomization scheme. The Cingal, TH and Placebo will be supplied by the Sponsor to the Investigational Sites for use in the trial. The third party will ship the CTM to the sites as needed. Specific instructions for ordering CTM will be provided to the sites.

13.2 Storage Requirements

The storage requirements for CTM are to be maintained in a secure controlled environment at room temperature below 77° F / 25° C. DO NOT FREEZE.

13.3 Instructions for Use

Instructions for Use will be provided in the Investigator's Brochure. The Investigator's Brochure document contains the following risk information:

13.3.1 Contraindications

Cingal[®]:

CINGAL® is composed of cross-linked hyaluronic acid and an ancillary corticosteroid TH. The following pre-existing conditions may constitute relative or absolute contraindications to the use of CINGAL®:

- Hypersensitivity to the active substance or to any of the excipients contained in CINGAL
- Pre-existing infections of the skin region of the intended injection site
- Infection of the index joint
- Systemic bleeding disorders

The ancillary medicinal substance, TH, is contraindicated in the case of:

- Hypersensitivity to TH
- Active tuberculosis
- Herpes simplex keratitis
- Acute psychoses
- Systemic mycoses and parasitoses (strongyloid infections)

TH:

Lederlon[®] 20 mg is a glucocorticoid (adrenal cortex hormone) that acts on the metabolism, the salt (electrolyte) balance and tissue functions. Glucocorticoids have anti-inflammatory and other therapeutic properties. The glucocorticoid in Lederlon[®] 20 mg is called TH.

Lederlon® 20 mg may NOT be used in the event of:

- Known hypersensitivity to TH or one of the following other ingredients in this medication: benzyl alcohol (9 mg per 1 ml), polysorbate 80, sorbitol (Ph. Eur.)
- Infections within or in direct proximity of the joint to be treated
- Joint inflammation due to bacterial infections (bacterial arthritis)
- Instability of the joint to be treated
- Tendency toward bleeding, either spontaneously or due to taking medications to inhibit coagulation (anticoagulants)
- Calcium deposits around joints
- Bone necrosis due to sporadic or persistent perfusion disorders (non-vascularized bone necrosis)
- Ruptured tendon
- Joint disease due to decreased pain perception in the joint (neuropathic arthropathy)

13.3.2 Anticipated Adverse Reactions

Reported adverse reactions associated with the IA use of combined Hyaluronic Acid and Triamcinolone Hexacetonide:

Single intra-articular injections of sodium hyaluronate combined with Triamcinolone Hexacetonide has been studied by Anika Therapeutics, Inc. in two Phase III clinical trials: Cingal 13-01, 16-02 and additionally the 39-week extension trial: Cingal 17-02

The most common reported adverse events associated are the following: arthralgia, joint swelling, warmth, range of motion decrease and injection site pain.

Incidences of rash, headache, dizziness, chills, hives, itching, nausea, muscle cramps, peripheral edema, and malaise have also been reported in association with intra-articular injections.

In Cingal 13-01, 16-02, and 17-02 the AEs that were possibly, probably and definitely related to the study injection for patients receiving Cingal were 2.0%, 7.6% and 0 % respectively [14-16]. These AEs were minor or moderate complications that required little or no treatment. These included injection site events, joint swelling, joint pain, and limb pain.

Reported adverse reactions associated with the IA use of corticosteroids:

Single intra-articular injections of Triamcinolone Hexacetonide have been associated with the following adverse reactions:

- Dermatologic: Whitening of the skin at the injection site, local fat atrophy.
- Musculoskeletal: Joint infection, joint swelling and pain several hours after injection, tendon rupture, pain, swelling, ligament damage.
- Neurological: Nerve damage.

• General: Infection, local bleeding, allergic reactions.

Anika Therapeutics, Inc. has conducted one Phase III trial utilizing Triamcinolone Hexacetonide (Lederlon) in Cingal 16-02 and additionally the 39-week extension trial: Cingal 17-02 [14, 15]. The AEs that were possibly, probably and definitely related to the study injection for patients receiving Triamcinolone Hexacetonide were 4.1% and 0 % respectively. These AEs were minor or moderate complications that required little or no treatment. These involved injection site pain and joint pain.

13.4 CTM Accountability

It is important to account for the disposition of all CTM received by a clinical site. Required information includes the date received, date injected, batch number, quantity injected, expiry date and the Subject who received the CTM.

The site will use a form to document CTM disposition which will be reviewed by the study monitor during routine monitoring visits. Each time CTM is dispensed, the following information should be recorded: the subject's initials, Subject ID, the Subject randomization number, date, the number of the CTM dispensed, and the initials of the person dispensing the CTM. At the termination of the study, Anika Therapeutics, Inc. will instruct sites on the disposition of unused CTM.

13.5 Emergency Unblinding

Unblinding should only occur when a SAE requires the allocation code in order to enable clinical treatments to be planned. The clinical team and Medical Monitor should assess the need for unblinding as time permits. The allocation details can then be provided. Upon unblinding, the site personnel should record withdrawal of the Subject and the allocation in the clinical trial notes.

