Subjects meeting the inclusion/exclusion criteria will be randomized to receive a single injection of Cingal®, Triamcinolone Hexacetonide (TH) or placebo in the Index knee. Since there is a difference in volume between Cingal®, TH and placebo, the treating physician will not be considered blinded. To maintain the double-blind design of the study, there will be a person assigned to the role of Treating Physician and one person assigned to the role of Blinded Evaluator. The Treating Physician, most often the PI, will administer the injection but will not participate in the evaluation of study treatment effectiveness. A second individual, designated as the Blinded Evaluator, is blinded to treatment and will complete the pre- and post-treatment Evaluator Global Assessment, knee exams and ROM measurements. To maintain the Subject blinding, the injection syringe will be prepared separate from the patient and the injection will be masked from the subject.

The Subject will be trained on how to complete the WOMAC, VAS Pain, NRS Pain, Patient Global Assessment and EuroQoL.

The Blinded Evaluator will collect and record AEs from the subjects and consult the Treating Physician only as needed in the management of AEs. The Blinded Evaluator will be a physician,

Anika Therapeutics, Inc. Cingal 19-01

research nurse, registered physiotherapist or physician assistant trained to perform the assessments outlined in the protocol (Section, 9.1 Schedule of Events).

Up to 40 sites in US may participate in the study to enroll and treat 231 subjects. Subject participation will last approximately 7 months with follow-up visits scheduled at weeks 1, 3, 6, 12, 18, and 26 after the treatment injection.

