10.5 Reporting

10.5.1 Adverse Events

Only AEs that occur during and after treatment (treatment emergent AEs) will be recorded. At each visit during the trial, AEs that have occurred since the previous visit must be recorded. All subjects will be questioned and evaluated for AEs or complications associated with the procedure. Complications of the injection include, but are not necessarily limited to: pain, swelling and/or inflammation at the injection site. The Investigator will determine the severity and relationship of each event, as defined above.

AEs observed during the course of this study, regardless of severity or relationship to the injection will

be recorded on the appropriate eCRF. Each reported complication/AE will also include the duration, action taken to address the AE, and the resolution status (e.g. ongoing, resolved). These subjects will continue to be evaluated for safety and efficacy at all scheduled follow-up points.

The Sponsor must report the results of an evaluation of an Unanticipated Adverse Device Effect (UADE) to relevant regulatory agencies and all reviewing IRBs and Investigators within timelines required by the regulatory agencies.

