10.5.2 Serious Adverse Events/Serious Adverse Device Effects/Serious Adverse Reactions

All SAE/SADE/SAR/ SUSAR must be reported to the Sponsor or designee within 24 hours of the investigative site becoming aware of its occurrence. This requirement is irrespective of whether the SADE/SAE is thought to be possibly related to the CTM/study procedure or not.

SAE/SADE/SAR/ SUSAR Reporting Procedures

Information such as the Investigator name, study name/protocol number, Subject ID number, the name of the SAE/SADE/SAR, the Investigator's assessment as to the relationship to the CTM/study procedure, and the reporting source should be included in the initial report. Any additional supporting documentation (e.g., autopsy report, hospital records, etc.) must be submitted to the Sponsor or designee. This also includes forwarding pertinent follow-up information (e.g., hospital discharge summary) as it becomes available. A completed SAE/SADE/SAR/ SUSAR form needs to be submitted with each follow-up. The Subject must be monitored carefully until the condition disappears, or the etiology is identified.

All SAE/SADE/SAR/ SUSAR will be entered into the EDC system. The EDC system will automatically notify the Medical Monitor and the Sponsor or designee.

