15.9 Protocol Adherence

The Investigator agrees to conduct the study according to the protocol and agrees that all persons delegated to perform study procedures will do so as well. The Investigator must read the protocol thoroughly and must follow the instructions exactly. Investigators shall propose to Anika Therapeutics, Inc. any appropriate modifications to the Protocol or of the use of the CTM. Any change should be agreed to by prior discussion between Anika Therapeutics, Inc. and the Investigator, with written protocol amendments made prior to affecting the changes agreed upon. The Investigator is not to conduct any protocol modifications without prior written permission from Anika Therapeutics, Inc. Investigator will refrain from implementing any modifications to the protocol without agreement from the Sponsor, IRB and FDA, if applicable. Each Investigator will be responsible for enrolling only those subjects who have met protocol eligibility criteria.

Deviations from the protocol include, but are not limited to, the use of prohibited medications or therapies, out of window visits, etc. All protocol deviations should be documented and explained. Major protocol violations are defined as those that could impact the efficacy evaluation such as a Subject is ineligible, missing key data, received an unauthorized treatment, etc. All subjects with protocol deviations will continue to be followed for safety and efficacy assessments. Analysis of study data will be done on both the ITT and PP populations.

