15.20 Subject Withdrawal

Each Subject is free to discontinue from the study at any time, for any reason. If a Subject discontinues the study, the Investigator will record the reason for withdrawal on the eCRF. Examples of reasons for premature withdrawal of a Subject from the study include:

- Inter-current illness that would, in the judgment of the Investigator, affect study assessment to a significant degree
- Subject noncompliance with follow-up assessments
- Subject request to withdraw
- Subject lost to follow-up
- Treatment failure
- Termination of the site's study participation by Anika Therapeutics, Inc., the institution, IRB or the Regulatory Authority
- Other (reason to be documented in the eCRF)

Every effort shall be made to have withdrawn subjects return for the required safety evaluations as detailed in the protocol.

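### Recording withdrawal when the code is broken for an SAE conflicts with the rule that subjects with AEs stay in scheduled safety and efficacy follow-up

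*Protocol*

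**What the plan says.** Protocol 13.5 sets a narrow trigger: "Unblinding should only occur when a SAE requires the allocation code in order to enable clinical treatments to be planned". It then states the consequence: "Upon unblinding, the site personnel should record withdrawal of the Subject and the allocation in the clinical trial notes".

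Protocol 10.5.1 sets the rule for subjects with adverse events. Its second paragraph opens "AEs observed during the course of this study, regardless of severity or relationship to the injection will" and goes on to require entry in the eCRF. It closes: "These subjects will continue to be evaluated for safety and efficacy at all scheduled follow-up points".

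Three other places bear on what withdrawal means here:

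- Protocol 7.2 describes the treatment: subjects are "randomized to receive a single injection of Cingal®, Triamcinolone Hexacetonide (TH) or placebo in the Index knee".
- Protocol 10.5.2 says of subjects with serious events: "The Subject must be monitored carefully until the condition disappears, or the etiology is identified".
- Protocol 15.20 says of those who leave the study: "Every effort shall be made to have withdrawn subjects return for the required safety evaluations as detailed in the protocol". Its example reasons for withdrawal do not name unblinding.

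For the analysis, Protocol 11.8 and SAP 4.5 take all treated subjects for safety. For the primary endpoint they take the ITT population with multiple imputation, and they treat any missing data as missing at random (MAR).

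**The concern.** The two rules give a site opposite instructions about the same subject. Up to 40 sites will apply them, and some may stop visits after a code break while others carry on.

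In a trial with continuing dosing, withdrawal after unblinding might at least coincide with stopping the product. Here no study treatment remains to stop, so the only thing withdrawal can end is observation.

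The subjects affected have had an event serious enough to need the code. Their missing week-26 scores would arise from a change in health. That is the situation which the SAP's case for MAR sets aside: it rests on people leaving for life reasons unconnected with health, and on missingness being unlikely to come from treatment or its lack of effect. The protocol would itself be producing missing data that its analysis plan assumes will not occur.

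**Working it through.** **1. Do the rules overlap?** Protocol 10.1 and 10.2 define a serious adverse event as an adverse event that meets seriousness criteria. Every subject unblinded under 13.5 therefore has an AE and falls under 10.5.1. That section covers all severities and carves out no exception for a broken code. The overlap is complete.

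**2. What would withdrawal change?**

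| | Under 10.5.1 | Under 13.5 read literally |
|---|---|---|
| Study treatment | Single injection, already given | Same |
| Scheduled efficacy visits | Continue | End, with no provision for later efficacy data |
| Scheduled safety visits | Continue | Best effort (15.20) |
| Follow-up of the SAE itself | Until resolved or explained (10.5.2) | Same |
| Data already collected | Analysed | Analysed |

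The firm loss is later efficacy data. Scheduled safety visits are weakened but not abolished.

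**3. What happens in the analysis?** Neither document removes an unblinded subject from the ITT or safety analyses. The subject stays in, with post-withdrawal scores imputed from a mixed effects repeated measures model. As described, that model does not include the SAE or the code break as a predictor. MAR could still hold in the technical sense if earlier scores carried the relevant information, but the reason the SAP offers for it does not apply to these subjects.

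**4. How large could it be?** Inputs from Protocol 11.1: 99, 99 and 33 subjects (total 231), difference 8 points, SD 20. Two-sided 5% level follows from 11.2 and 11.5.

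Power ≈ Φ(δ / (σ√(2/n)) − 1.96)

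- Plan's own figure: 8 / (20 × √(2/99)) = 2.814; Φ(2.814 − 1.96) = 80.4%, matching the stated 80%. For 10 points the result is 94.0%, matching the stated figure of over 90%.

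The documents give no unblinding rate, so the rates below are assumptions. The last column takes the worst case for precision: all week-26 data from these subjects lost, with nothing recovered by imputation.

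| Assumed share unblinded and withdrawn | Subjects of 231 | Power for 8 points |
|---|---|---|
| 0 | 0 | 80.4% |
| 0.25% | 0.6 | 80.3% |
| 1% | 2.3 | 80.0% |
| 2% | 4.6 | 79.6% |
| 5% | 11.6 | 78.3% |

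One subject is 1/99 = 1.0% of a main arm and 1/33 = 3.0% of placebo. As a crude ceiling on bias, suppose one imputed week-26 score were wrong by the full 100 mm scale. It would shift an unadjusted arm mean by 100/99 = 1.0 mm in a main arm and 100/33 = 3.0 mm in placebo. Real errors should be well below that, because imputation uses the subject's earlier scores.

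For comparison, SAP 4.5 cites under 1% missing data in previous studies. That is 0.01 × 231 = 2.3, or about two subjects here. One to three code-break withdrawals would be 1/231 = 0.4% to 3/231 = 1.3%, as many as all the missing data the plan expects.

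**The case against.** The strongest reply is that 13.5 is a specific emergency rule and can be read as an exception to the general rule in 10.5.1. Follow-up under 10.5.1 is not absolute elsewhere: 15.20 permits withdrawal for intercurrent illness that would affect assessment, and for other documented reasons. The post-treatment text in 9.8 leaves efficacy inclusion after significant complications to case-by-case decision. This has some force, but 13.5 does not present itself as an exception, and neither 15.20 nor 9.8 mentions a code break.

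A second reply is that 13.5 only tells the site what to write in the notes and does not say that visits stop. That is possible. It makes the sentence ambiguous, which is itself a reason to clarify it.

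A third is that the primary endpoint is self-reported pain, so scores given with allocation known are open to expectation bias. This stands as a real cost. Flagging those scores and running a sensitivity analysis deals with it better than not collecting them.

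A fourth is rarity. The Treating Physician is unblinded by design and can be consulted on AEs, and Protocol 4 reports that all SAEs in earlier trials (642 subjects given Cingal) were judged unrelated. This also stands, and it limits the point to a minor one.

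A reader might go further and infer that the rule discards outcome and safety data. The documents do not support that. Nothing deletes collected data, and 10.5.2 and 15.20 preserve much of the safety follow-up. A reader might also cite Protocol 15.9 ("All subjects with protocol deviations will continue to be followed for safety and efficacy assessments") as a second contradiction. It does not apply, because a code break carried out under 13.5 is a prescribed procedure and not a protocol deviation.

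**Conclusion.** The conflict between 13.5 and 10.5.1 is real and unreconciled. Followed literally, 13.5 ends scheduled efficacy follow-up, and reduces scheduled safety visits to best effort, for subjects unblinded because of an SAE. It creates avoidable week-26 gaps that the MAR argument in SAP 4.5 does not cover.

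The effect on power is negligible, at most about two percentage points even if 5% of subjects were affected (80.4% to 78.3%). The likely number is far smaller, but that is a judgement, since the documents give no rate. The conclusion rests on reading the recorded withdrawal as withdrawal from the study. If it means documentation only, the remaining defect is unclear wording. This is a minor point, worth correcting because the correction is cheap.

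**What to change.** Reconcile Protocol 13.5, 10.5.1 and 15.20:

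- Record a code break in source and eCRF as an event (date, reason, who learned the allocation), and not by itself as withdrawal from the study.
- State that scheduled data collection continues if the subject agrees.
- Flag every assessment made after the subject or the Blinded Evaluator knows the allocation.
- Add a sentence to SAP 4.5 giving the number of such subjects by arm and a sensitivity analysis, for example with flagged scores used as observed and then set to missing and imputed.

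This concerns data collection only. It says nothing about care of the event or when the code should be broken.

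The cost is about one sentence in the protocol with matching cross-references, a short eCRF entry and one sentence in the SAP. The downside is a few self-reported scores given with allocation known.
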